### 8.3.3 Exploratory Analyses

Responses to the Post whitening questionnaire (separate questions and total score) will be analyzed between product groups using an independent t-test.

The change from screening in DHEQ total and domain scores at Visit 3 and Visit 4 will be analyzed between groups using separate ANCOVA models with study product as a fixed effect and the respective DHEQ total or domain score at screening as a covariate. The least square means (with SE and 95% CI) for each study product will be presented along with the difference (with SE and 95% CI).

All tooth-sensitivity endpoints will be summarized further, split by the whether the subject had confirmed DH at the screening assessment. Additional statistical testing may be performed using similar methods to those performed on the full mITT dataset.

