## 4 STUDY POPULATION

### 4.1 Type and Planned Number of Subjects

Healthy volunteers of either sex and any gender, aged 18 – 65 years will be recruited who wish to have their teeth whitened and meet all the inclusion/exclusion criteria.

Sufficient subjects will be screened to randomize approximately 90 subjects (approximately 30 per treatment group) to ensure approximately 88 evaluable subjects complete the study (assuming a 2% dropout rate).

This study can fulfill its objectives only if appropriate subjects are enrolled. The following eligibility criteria are designed to select subjects for whom participation in the study is considered appropriate. All relevant medical and non-medical conditions should be taken into consideration when deciding whether a subject is suitable for this protocol.

Subject eligibility to participate in the clinical study should be reviewed and documented by an appropriate member of the investigator's study team before subjects are included in the study.

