### **6.3.3 Dentine Hypersensitivity Experience Questionnaire (DHEQ)**

A 'short form' DHEQ-15 will be completed by each eligible subject at Visits 1, 2 (prior to first application of tooth bleaching), 3 and 4.

The DHEQ-15 is divided into two sections - Section 1 asks questions about 'your sensitive teeth and the impact it has on your everyday life'; Section 2 asks questions about 'the ways in which the sensations in your teeth affect you in your daily life' grouped into the following domains.

- Restrictions (Section 2, Q1-3)
- Adaptation (Section 2, Q4-6)
- Social Impact (Section 2, Q7-9)
- Emotional Impact (Section 2, Q10-12)
- Identity (Section 2, Q13-15)

At Visit 1 all questions will be answered - Section 1 (Q1-9) and Section 2 (Q1-15)

At Visits 2, 3 and 4 Section 1 (Q7-9 only) and Section 2 (Q1-15) will be answered.

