### **7.3 Blinding and Randomization**

Subjects will be randomized into the study provided they have satisfied all subject selection criteria.

Subjects will be randomized to one of the study products with a 1:1:1 allocation ratio using an Interactive Response Technology (IRT). The randomization schedule will use a stratified randomly permuted block design. Stratification will be based on the clinically diagnosis of DH at -Screening (Yes/No). Approximately 45% (40-50%) of randomized subjects should have clinically-confirmed DH.

Study products will be provided to subjects in individual packs (cartons); each carton will contain overwrapped tubes of study product. The carton and tubes of study product will be labelled with the same unique container number. Subjects will be assigned to container numbers associated with cartons containing only their randomized study product using an Interactive Response Technology (IRT); product codes will not be used.

Returned study products should not be re-dispensed to any subject.

This study is described as examiner-blind (the clinical examiner will be blinded to the product received).

To ensure the examiner remains blinded throughout the study, staff involved in the preparation and dispensing of study products will work in a separate area.

Subjects will be instructed not to remove study products from the opaque bags provided/cartons outside of the dispensing room, while at the study site. Dispensing staff will not be involved in any efficacy/safety assessment procedures during the study.

Site staff, study statistician(s), data management staff and other employees of the sponsor and vendors acting on behalf of the sponsor, who may influence study outcomes will be blinded to the product allocation.

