## 8 STATISTICAL CONSIDERATIONS AND DATA ANALYSES

### 8.1 Sample Size Determination

No formal sample size calculation was performed for this study. The sample size requirement of approximately 30 randomized subjects per arm is based on feasibility due to the exploratory (proof-of-principal) nature of the study, whilst ensuring an adequate number of subjects to address the study objectives ([Kieser and Wassmer, 1996](#)).

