## 9.13 Post-Whitening Questionnaire.

To be completed at Visit 3 after the completion of the peroxide tooth whitening.

Please tick the boxes that best answers the statements:

	Strongly Agree	Agree	Agree a Little	Neither Agree nor Disagree	Disagree a Little	Disagree	Strongly Disagree
	(7)	(6)	(5)	(4)	(3)	(2)	(1)
1) I am satisfied with the results of my tooth whitening.							
2) I found it inconvenient to switch my toothpaste for this study.							
3) I found my teeth to be painful during the tooth whitening treatment.							
4) I would recommend tooth whitening to a friend or relative.							
5) I would consider further tooth whitening treatments in the future.							
6) I had to change the way I ate or drank certain things during the tooth whitening treatment.							
7) Having sensations in my teeth during tooth whitening took pleasure out of eating and drinking .							
8) Having sensations in my teeth during tooth whitening was worrying to me.							

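### The t-test for the Post-Whitening Questionnaire leaves out the DH stratum and any baseline covariate; adding them would be a minor, nearly free gain in precision if they are prognostic.

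*Combined protocol and SAP*

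**What the plan says.** - **The test.** Section 8.3.3 states that the questionnaire, by separate question and by total score, "will be analyzed between product groups using an independent t-test". It names no covariate or stratum and, unlike the DHEQ analysis that follows it, no confidence interval.
- **The design.** Section 7.3: "Stratification will be based on the clinically diagnosis of DH at -Screening (Yes/No"). The DH stratum is large: "Approximately 45% (40-50%) of randomized subjects should have clinically-confirmed DH". Also: "Subjects will be randomized to one of the study products with a 1:1:1 allocation ratio".
- **The items.** The Post-Whitening Questionnaire (Section 9.13) is given once, at Visit 3. Item 3 asks whether teeth were "painful during the tooth whitening treatment". Items 6-9 cover changed eating or drinking, lost pleasure in eating, and worrying or unpleasant sensations.
- **The available baseline.** Section 6.3.3: "A 'short form' DHEQ-15 will be completed by each eligible subject at Visits 1, 2 (prior to first application of tooth bleaching), 3 and 4". Section 3 places the Visit 1 questionnaires before stratification and randomization.
- **Size and power.** Section 8.1: "No formal sample size calculation was performed for this study". Section 4.1 plans to "randomize approximately 90 subjects (approximately 30 per treatment group) to ensure approximately 88 evaluable subjects complete the study (assuming a 2% dropout rate").

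**The concern.** When randomization is balanced within strata and the stratum predicts the outcome, an analysis that ignores the stratum leaves the between-stratum variance in its error term, although the design has already removed it from the product comparison. The reported standard error is then larger than the true one, and the test rejects less often than its nominal level.

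There is reason to think that DH could matter here. The plan stratifies on it, sets a quota for it and fits it in every tooth-sensitivity model of Section 8.3.2. Items 3 and 6-9 ask about a closely related experience. The same holds for the screening DHEQ, whose Section 2 asks about care over food, anxiety about sensations, and irritating or annoying sensations.

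At stake is the sensitivity of the only planned test for the exploratory objective on subjects' experience of bleaching, with about 30 subjects per arm.

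**Working it through.** **1. The plan's own figure.** 88 / (1 - 0.02) = 89.8, so 90 randomized, or 30 per arm. This reproduces Section 4.1. No power, effect size or SD is stated for any endpoint, so every effect input below is an assumption.

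**2. Adjustment terms across the plan (Sections 8.3.2 and 8.3.3).**

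| Endpoint | DH stratum | Baseline covariate |
|---|---|---|
| VAS, LMS, Bothersomeness | yes | screening value of the same scale |
| Sensitivity-free days, analgesic days | yes | none |
| VITA shade | no | screening shade |
| DHEQ | no | screening DHEQ |
| Post-Whitening Questionnaire | no | none |

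The last row is the only one with no adjustment term.

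**3. Effect of leaving out DH, by formula.** Let p = 0.45 be the DH share and d the assumed DH difference in within-stratum SDs. The share of variance due to DH is R² = p(1-p)d² / (1 + p(1-p)d²), with p(1-p) = 0.2475. The ratio of adjusted to unadjusted interval width is √(1 - R²).

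- d = 0.5: R² = 0.0619 / 1.0619 = 0.058; ratio 0.970.
- d = 1.0: R² = 0.2475 / 1.2475 = 0.198; ratio 0.895.

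With the DH share at 40% or 50% the ratio is 0.970-0.971 at d = 0.5 and 0.894-0.898 at d = 1.0.

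The t-test's critical value on 58 df is 2.002. Because the reported SE is too large by 1/ratio, the effective critical value is 2.002 / 0.970 = 2.06 (d = 0.5) or 2.002 / 0.895 = 2.24 (d = 1.0). The two-sided tail areas on 58 df are about 4.4% and 2.9%.

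**4. Adding a screening score.** If the score has within-stratum correlation ρ with the item, the width ratio is √[(1 - ρ²) / (1 + 0.2475d²)].

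- d = 0.5, ρ = 0.3: √(0.91 / 1.0619) = 0.926.
- d = 1.0, ρ = 0.5: √(0.75 / 1.2475) = 0.775.

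**5. Simulation.** 6,000 trials per scenario; 90 subjects, 40 with DH; stratified permuted blocks of 6 (assumed, as no block size is given); normal outcomes; two of the three arms compared. Power is at a true difference of 0.6 within-stratum SD. The adjusted model has DH only where ρ is marked as not used; otherwise it has DH and the baseline score.

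| d | ρ | Type I error, t-test | Type I error, adjusted | Width ratio | Power, t-test | Power, adjusted |
|---|---|---|---|---|---|---|
| 0.5 | not used | 4.7% | 5.2% | 0.97 | 60% | 63% |
| 1.0 | not used | 2.9% | 5.1% | 0.89 | 54% | 63% |
| 0 | 0.4 | 4.8% | 4.8% | 0.93 | 63% | 69% |
| 0.5 | 0.3 | 4.2% | 5.1% | 0.93 | 61% | 66% |
| 1.0 | 0.5 | 3.3% | 5.1% | 0.78 | 53% | 75% |
| 0 | 0 | 5.0% | 5.2% | 1.01 | 63% | 62% |

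A second simulation (4,000 trials, DH counts fixed at 13, 14 and 13 per arm) gave t-test type I error of 4.2% at d = 0.5 and 3.2% at d = 1.0 with DH alone, and a width ratio of 0.78 for the strong case.

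The row with d = 0 and ρ = 0.4 separates the two mechanisms. Omitting a prognostic score that is not a stratification factor leaves type I error at its nominal level and costs only precision and power. Conservatism comes from the DH stratum alone.

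**The case against.** The case for leaving the plan alone has real parts.

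- **No own baseline.** The questionnaire is given only at Visit 3. Each baseline covariate elsewhere is the screening value of the measure under analysis, and none exists here. The DHEQ is a different instrument and would be a proxy. This stands, and it may explain the omission of a baseline score. It does not explain the omission of DH.
- **DH is missing elsewhere too.** The VITA and DHEQ models also leave it out, so a reader who infers that this test breaks a plan-wide rule goes too far. What sets it apart is that it has no adjustment term at all.
- **Pain is analysed with adjustment elsewhere.** The VAS, LMS, Bothersomeness, day-count and DHEQ analyses all adjust. The study does not depend on this t-test for its evidence on sensitivity during bleaching.
- **Favourable assumptions.** The large gains need a 1 SD DH effect plus a correlation of 0.5 over and above DH. The simulations use normal outcomes, whereas each item is a single 7-point rating. Items 1, 2, 4 and 5 may gain little.

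A reader might also infer that the planned comparisons certainly have over-wide intervals. The documents do not support that: they give no prognostic strength, and Section 8.3.3 promises no interval for this test. Nor does omitting the DHEQ score cause over-coverage.

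None of this makes the t-test the better choice. If neither covariate is prognostic, adjusting costs about one percentage point of power.

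**Conclusion.** The point holds as a conditional efficiency gain on an exploratory endpoint, and it is minor. If DH strata differ by 0.5 to 1 SD on the pain and sensation items, the t-test's type I error is about 4-5% down to 3%, and fitting DH narrows the interval by about 3-10%. With a prognostic screening DHEQ score as well, the width ratio runs from about 0.93 (DH 0.5 SD, correlation 0.3) to 0.78 (DH 1 SD, correlation 0.5). If neither predicts the item, nothing material changes (ratio 1.01). These results rest on assumed effect sizes, 30 per arm and normal outcomes.

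It would be wrong to read this as a validity error. The test is at worst conservative, the study is exploratory with no formal success criterion, and no figure stated in the plan is incorrect.

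**What to change.** In Section 8.3.3, replace the independent t-test with an ANCOVA for each Post-Whitening item and for the total score. Fit study product and DH diagnosis at screening (yes/no) as fixed effects, and the screening DHEQ-15 Section 2 total as covariate. Report least-squares means and all pairwise product differences with SE and 95% CI. This also settles which pairs of the three arms are compared, which a two-sample test leaves open.

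Do not adjust for anything measured at Visit 2, including the pain-concern item of the Whitening History Questionnaire. By then subjects have used their product for two weeks; Section 8.3.2 gives the same reason for leaving out Visit 2 sensitivity scores.

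The cost is one sentence and two model degrees of freedom (58 to 56 in a two-arm comparison), with no new data, visits or staff. Section 8.3 allows such a clarification to be documented in the blinded data review before database lock and unblinding.

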To explore subject's oral-health related quality of life during peroxide tooth bleaching when simultaneously using either a 5% NovaMin-containing dentifrice, a 5% KNO 3 -containing dentifrice or a regular fluoride dentifrice.	Change from screening in responses from the Dentine Hypersensitivity Experience Questionnaire (DHEQ) during the tooth bleaching period (Visit 2-3) and for the two weeks post tooth bleaching (Visit 3-4)
To investigate the ability of a 5% NovaMin-containing dentifrice to reduce self-perceived tooth sensitivity as measured by a subject-completed tooth sensitivity questionnaire compared to a 5% KNO 3 -containing dentifrice and a reference dentifrice for 2 weeks from the	
Responses from the DHEQ and tooth sensitivity questionnaire during the tooth bleaching period (Visit 2-3) and separately for the 2 weeks post tooth bleaching (Visit 3-4) in:-
 
 
• Mean VAS
 

Property of Haleon- Confidential

May not be used, divulged, published or otherwise disclosed without the consent of Haleon

end of tooth bleaching separately for those subjects with and without clinically-confirmed dentine hypersensitivity (DH).	
 
• Mean LMS
 
• Mean Bothersomeness
 
• % tooth sensitivity-free days
 
• % days analgesics used to alleviate tooth sensitivity
 
• Change from screening in DHEQ
 

To explore subject's experience of peroxide tooth bleaching when simultaneously using either a 5% NovaMin-containing dentifrice, a 5% KNO 3 -containing dentifrice or a regular fluoride dentifrice.	Post-whitening questionnaire

No formal success criterion has been defined for this exploratory study; however, if the NovaMin dentifrice provides sensitivity protection during tooth bleaching, it would be expected that subject perceived tooth sensitivity (measured by the subject completed sensitivity questionnaires) for the NovaMin dentifrice would be directionally superior to the reference dentifrice during the study period.

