The usage regimen of twice daily brushing (morning and evening) will be the same for all subjects and is based on widely recommended oral hygiene practice/typical consumer habit. Study subjects will be required to brush for 1 timed minute with their assigned study dentifrice on each brushing occasion. On each brushing occasion, the toothbrush will be dosed with a ribbon of dentifrice (covering the entire length of the toothbrush), in line with the product labelling for the study dentifrices.

The test dentifrice is indicated for DH. However, it is anticipated that it will be purchased both by consumers with DH and those who do not, but who are recommended (by a dental health care professional) to use a sensitivity dentifrice prior to, during and post peroxide dental bleaching treatment. A mixed population of those with clinically-diagnosed DH and those with no DH symptoms is therefore appropriate. Subjects will be stratified according to their DH status [DH positive or negative (DH positive defined as at least 1 tooth with a Schiff score  $\geq 2$ )] to ensure a balanced population across treatment groups.

The subjects in this study who have self-diagnosed DH will be clinically evaluated to confirm their DH status. DH is prevalent at 30-50% of the population ([West, 2023](#)) and the enrollment

to this study is designed to mirror this with a requirement that approximately 45% [with a window of 40-50%] of the randomized subjects to have clinically confirmed DH.

Demography information will be recorded as part of this study, including age, race and gender. In accordance with the United States Food and Drug Administration (US FDA) guidelines ([FDA, 2005](#)) the ethnicity of subjects will also be captured.

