3. The tooth sensitivity questionnaire will evaluate overall tooth sensitivity with LMS and VAS assessments. The questionnaire will be completed for the duration of tooth bleaching treatment and for 2 weeks post completion of tooth bleaching.
4. The supplied tooth bleaching kit will be used once under supervision at the study site and then once per day at home (for a total of 7 days) in accordance with the manufacturer's instructions.
5. Female subjects of child-bearing potential only.
6. DH assessments to be administered only to subjects with self-diagnosed DH.
7. Stratification will be based on clinically-diagnosed DH (Y/N) at screening.
8. Sections 1&2 to be completed at V2. Section 1 (questions 7-9 only) and Section 2 to be completed at V3&4. DHEQ to be completed at the study site.

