### 8.3.2 Secondary Endpoint Analyses

The VAS score for tooth sensitivity for the first 7 days during the tooth bleaching period will be analyzed using a Mixed Model with Repeated Measures (MMRM), with study product, DH diagnosis at screening (yes/no), days of bleaching and study product by days of bleaching interaction as fixed effects. The VAS score at screening will also be included as a covariate. Subject will be included as a repeated measure with compound symmetry covariance structure. Kenward Rogers degrees of freedom approach will be applied ([Kenward and Roger, 1997](#)). The overall (across all days) least square means (with SE and 95% confidence intervals [CI]) for each study product will be presented along with the difference (with SE and 95% CI).

A separate MMRM will be applied to evaluate the pairwise differences between products for each day. This will be identical to the above MMRM but subject will be included as a repeated measure with unstructured covariance matrix. In case of convergence issues, the Toeplitz, Autoregressive (1), Compound Symmetry covariance structures will be applied until convergence is attained (all heterogeneous versions first and then the same sequence of homogeneous versions). The least square means (with SE and 95% CI) for each study product will be presented along with the pairwise differences (with SE and 95% CI) between products for each day using the appropriate contrasts from the MMRM results.

As a further sensitivity analysis, the mean VAS score for tooth sensitivity over the tooth-bleaching period (Visit 2 [at home] to Visit 3) for a subject will be analyzed using an Analysis of Covariance (ANCOVA) model will be used with study product and DH diagnosis at screening (yes/no) as fixed effects and the VAS score at screening as a covariate. The least square means (with SE and 95% CI) for each study product will be presented along with the difference (with SE and 95% CI).

The LMS and the Bothersomeness scores during the tooth-bleaching period will be analyzed and presented in identical fashion to the VAS scores endpoint using the same MMRMs and ANCOVA (replacing the respective screening result as a covariate).

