For the % tooth sensitivity-free days and the % days analgesics used to alleviate tooth sensitivity during the tooth bleaching period, a negative binomial model will be applied to the number of days with the event. Study product and DH diagnosis at screening (yes/no) will be fitted as fixed effects. An offset variable for the number of days the daily question related to tooth sensitivity (Yes/No) was completed during the tooth bleaching period will be included to adjust for missing days in estimating the rates. The back transformed rates for each study product group and ratios between rates will be presented along with 95% CIs.

Each analysis assessing tooth sensitivity during the tooth bleaching period will also be applied to the same tooth sensitivity endpoints during the post-tooth bleaching period.

The tooth sensitivity scores at Visit 2 (prior to bleaching) will not be included in the analyses as a covariate because it is expected that the randomized product group at Screening will have

Property of Haleon- Confidential

May not be used, divulged, published or otherwise disclosed without the consent of Haleon

a causal effect on this outcome. Low tooth sensitivity following tooth bleaching should not be adjusted in the analysis for low tooth sensitivity at Visit 2, as this could be lower in general for subjects randomized to test and reference dentifrice groups at Visit 1.

An ANCOVA model will be applied to analyze the change in the mean VITA Shade score from pre- to post-tooth bleaching (Visit 2-3) with study product as a fixed effect and the mean VITA-Shade color score at screening fitted as a covariate. The least square means (with SE and 95% CI) for each study product will be presented along with the difference (with SE and 95% CI).

The assumption of normality and homogeneity of variance in each parametric test applied (i.e. ANCOVA / MMRM) will be investigated. In case of violation of these assumptions, a suitable non-parametric test will be performed, and results will be provided to support the parametric results.

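### The DHEQ ANCOVAs at Visits 3 and 4 leave out DH diagnosis, the stratification factor that every tooth-sensitivity model includes, so their intervals are conservative if DH matters beyond the screening score

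*Combined protocol and SAP*

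**What the plan says.** DH status at screening is the only stratification factor. Footnote 7 to the Schedule of Activities (Section 5.1) states: "Stratification will be based on clinically-diagnosed DH (Y/N) at screening". Section 7.3 repeats this and specifies permuted blocks with 1:1:1 allocation. Section 3 gives the purpose: "to ensure a balanced population across treatment groups".

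Section 8.3.2 carries that factor into all the tooth-sensitivity models:

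- The overall VAS MMRM is fitted "with study product, DH diagnosis at screening (yes/no), days of bleaching and study product by days of bleaching interaction as fixed effects", with screening VAS as a covariate. The by-day MMRM has the same fixed effects.
- The mean-VAS ANCOVA uses "study product and DH diagnosis at screening (yes/no) as fixed effects and the VAS score at screening as a covariate".
- LMS and bothersomeness use the same models, each with its own screening value.
- For the negative binomial models of sensitivity-free days and analgesic days: "Study product and DH diagnosis at screening (yes/no) will be fitted as fixed effects".
- All of these are repeated for the post-bleaching period.

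For DHEQ, Section 8.3.3 specifies only "separate ANCOVA models with study product as a fixed effect and the respective DHEQ total or domain score at screening as a covariate". DH diagnosis does not appear. Table 2-1 also lists DHEQ change separately by DH status, and Section 8.3.3 permits optional testing within that split. Neither puts DH into the overall comparison between products.

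**The concern.** When randomization is stratified, the true sampling variance of a product difference already benefits from the balance in the stratification factor. A model that leaves the factor out does not know this. Any outcome variation tied to the factor stays in the residual, the standard error is overstated, and the nominal 95% interval covers more than 95% of the time. The direction is safe, but the interval is wider than the design warrants.

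The plan does not treat the screening score as a stand-in for DH elsewhere: the VAS, LMS and bothersomeness models contain both. DHEQ is an instrument for dentine hypersensitivity, and Section 3 cites it as validated for that condition, so DH is at least as natural a covariate for DHEQ as for VAS. The plan explains another covariate choice, the exclusion of Visit 2 scores in Section 8.3.2, but gives no reason for this one.

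At stake is how tight the reported quality-of-life comparisons are, in a trial of about 30 subjects per arm sized on feasibility. The validity of those comparisons is not in question.

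**Working it through.** **Inputs from the documents.** About 90 subjects randomized, 2% dropout, about 88 evaluable (Section 4.1); three arms, 1:1:1, stratified permuted blocks, about 45% with DH (Section 7.3); 95% CIs (Section 8.3.3); DHEQ total and five domains (Section 6.3.3).

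**The plan's own figure.** 90 × (1 − 0.02) = 88.2, which agrees with the stated 88.

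**Models affected.** (1 total + 5 domains) × 2 visits = 12.

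**Residual degrees of freedom at 88 subjects.** As planned: 88 − (1 intercept + 2 product + 1 covariate) = 84. With DH added: 83.

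**Assumptions, because the documents give no DHEQ SD and no DH-DHEQ association.** The partial R² of DH given the screening score is varied from 0 to 0.20. The screening score is taken to be δ = 0.8 within-group SD higher in DH subjects.

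**Interval width.** Stratification balances DH across products, so the ratio of widths (without DH to with DH) is close to

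width ratio = [1/√(1 − R²)] × t(0.975, 84)/t(0.975, 83).

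At R² = 0 the bracket is 1 and the t ratio gives 0.9998. At R² = 0.10 it is 1.0541 × 0.9998 = 1.054.

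**DH effect that each R² implies.** With p = 0.45, p(1 − p) = 0.2475. The squared correlation of DH with the screening score is

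ρ² = δ²p(1 − p)/[1 + δ²p(1 − p)] = 0.1584/1.1584 = 0.137.

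The DH effect beyond the screening score, in residual SDs of the model that includes DH, is

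d = √{[R²/(1 − R²)]/[p(1 − p)(1 − ρ²)]}.

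At R² = 0.20, d = √(0.25/0.2137) = 1.08. With δ = 0.4 or 1.2 it would be 1.02 or 1.17.

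**Simulation.** 90 randomized (40 DH, 50 non-DH), blocks of 6 within stratum (block size assumed), 2 subjects dropped at random, screening-score slope 0.5 (assumed), 40,000 trials per setting, Monte Carlo SE about 0.001.

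| Partial R² (assumed) | Width ratio, formula | Width ratio, simulated | DH effect beyond screening score (SD) | Coverage without DH | Coverage with DH |
|---|---|---|---|---|---|
| 0 | 0.9998 | 0.999 | 0 | 0.950 | 0.950 |
| 0.02 | 1.010 | 1.009 | 0.31 | 0.952 | 0.949 |
| 0.05 | 1.026 | 1.026 | 0.50 | 0.955 | 0.950 |
| 0.10 | 1.054 | 1.055 | 0.72 | 0.958 | 0.949 |
| 0.20 | 1.118 | 1.122 | 1.08 | 0.968 | 0.950 |

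Mean bias was at most 0.003 SD throughout. Changing δ to 0.4 or 1.2, or the block size to 3 (20,000 trials each), gave coverage without DH of 0.958 to 0.960 at R² = 0.10 and 0.964 to 0.971 at R² = 0.20.

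**Is stratification the cause?** In a separate simulation at R² = 0.20 (20,000 trials), the planned model covered 96.7% under stratified blocks and 95.0% under unstratified randomization. The excess coverage therefore comes from stratifying without adjusting. In the stratified case the mean model SE was 0.263 against a true SE of 0.240, which shows the overstatement directly.

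**The case against.** The strongest reply is that nothing in the documents shows the omission matters.

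- **Size.** The screening DHEQ score is already in the model and measures the impact of sensitivity directly. DH status is a coarse yes/no: it is assessed only in subjects who report DH themselves, and it needs a qualifying tooth among those to be bleached, whereas DHEQ asks about the whole mouth. A residual effect of 0.7 to 1.1 SD is hard to motivate, and 0 to 3% of width is at least as plausible. This stands. DH on the bleached teeth could still predict how bleaching is experienced, so a zero effect cannot be assumed either.
- **Nature of the loss.** Stratified blocks already balance DH, so the estimate itself loses little. In a simulation of 8,000 trials per setting, the true SD of the product difference without and with DH was 0.268 and 0.268 at R² = 0.05, and 0.268 and 0.261 at R² = 0.20. The mean reported SEs were 0.269 against 0.262, and 0.294 against 0.262. This also stands: the issue is mainly an over-wide reported interval, not a noisier estimate.
- **Pattern rather than slip.** The shade ANCOVA and the post-whitening t-test also omit DH, so the plan may have reserved the term for tooth-sensitivity outcomes. That is possible, but it is not stated. No criticism is made of those two analyses: the documents show no link between DH and shade change, and the t-test is a different method. DHEQ differs because it concerns dentine hypersensitivity itself.
- **Consequence.** DHEQ is exploratory, the study has no formal success criterion, and its directional expectation concerns the sensitivity questionnaires. This stands and caps the importance of the point.
- **Split by DH status.** It will show whether DH matters, but it leaves the overall DHEQ model unchanged.

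**Conclusion.** The concern holds and is minor. The omission is plain in the text, and so is its inconsistency with the tooth-sensitivity models. The direction is firm: the product comparisons stay unbiased, type I error is not inflated, and the intervals are too wide if DH carries information on DHEQ beyond the screening score.

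The size is not firm. It runs from nothing to a few percent of interval width over partial R² values of 0 to 0.05. It reaches 5% to 12% only if DH has a large residual effect, which the documents neither support nor exclude. These figures rest on the assumed R² range and 88 evaluable subjects; the simulated coverage also depends on the assumed block size, screening-score slope and δ. Varying block size and δ changed the coverage only slightly.

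**What to change.** Add DH diagnosis at screening (yes/no) as a fixed effect to the DHEQ total and domain ANCOVAs at Visits 3 and 4, and keep the respective screening score as covariate. Adding it to the shade ANCOVA would be optional, for consistency only. If DH was left out of the DHEQ models on purpose, one sentence giving the reason would settle the point.

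The cost is one term in each of 12 models, using data already collected for stratification, and one residual degree of freedom per model (84 to 83). If DH adds nothing, the intervals widen by about 0.1%. Section 8.3 allows such a clarification to be recorded in the blinded data review documentation before database lock and unblinding; making it then avoids choosing the covariate after the results are known.
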